## 8.2.8. Pregnancy

- Pregnancy data from female participants and female spouses/partners of male participants will be collected from the first dose of study drug until 3 months after the last dose of study drug. Any female participant who becomes pregnant while participating in the study will be discontinued from the study drug. If a pregnancy is reported, the Investigator must immediately inform Alexion within 24 hours of awareness of the pregnancy and follow the procedures outlined in Section 10.5.
- For all Alexion products, both in development or postapproval, exposure during pregnancy must be recorded and the pregnancy followed, until the outcome of the pregnancy is known (ie, spontaneous miscarriage, elective termination, normal birth, or congenital abnormality), even if the participant discontinues the study drug or withdraws from the study. The corresponding infant must be followed-up for 3 months postpartum.
- Pregnancy is not considered as an AE (Section 10.5.3) unless there is a suspicion that the study drug may have interfered with the effectiveness of a contraceptive medication. However, complications of pregnancy and abnormal outcomes of pregnancy are AEs and may meet the criteria for an SAE (eg, ectopic pregnancy, spontaneous abortion, intrauterine fetal demise, neonatal death, or congenital anomaly) (Section 8.3). Elective abortions without complications should not be reported as AEs.

#### **8.2.9.** Infusion Site Evaluation

Infusion site evaluations will be performed at the time points specified in the SoA (Section 1.3). Infusion site reactions (eg, induration  $\leq 1$  cm in size) will not be listed as an AE unless they persist for more than 24 hours.

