#### 8.3.5.1. Infusion-Related Reaction

Infusion-related reactions to mAbs include both immune mediated and non-immune mediated reactions. Symptoms of IRRs may include flushing, alterations in heart rate and BP, dyspnea, bronchospasm, back pain, fever, urticaria, edema, nausea, and all types of rashes. Anaphylaxis is recognized as a severe, life-threatening, generalized, or systemic reaction. IRRs usually develop during drug infusion, or within hours of infusion, although may be delayed for up to 24 hours. Most IRRs are mild to moderate in severity.

Refer to Section See Section 10.4 for guidance on management of IRRs.

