## 10.4. Appendix 4: Guidelines for Grading and Management of Allergic or Infusion-Related Reactions

Infusion-associated reactions are a potential risk with the use of monoclonal antibodies; these reactions can be nonimmune or immune mediated (eg, hypersensitivity reactions). Signs and symptoms may include headache, fever, facial flushing, pruritus, myalgia, nausea, chest tightness, dyspnea, vomiting, erythema, abdominal discomfort, diaphoresis, shivers, hypertension, lightheadedness, hypotension, palpitations, and somnolence. Signs and symptoms of hypersensitivity or allergic reactions may include hives, swollen face, eyelids, lips, or tongue, or trouble with breathing.

All infusion-associated reactions will be reported to the Investigator and qualified designee. The Investigator and qualified designee are responsible for detecting, documenting, and recording events that meet the definition of AE or SAE and remain responsible for following up events that are serious, considered related to the study drug, or study procedures; or that caused the participant to discontinue ALXN1830.

Definitions and procedures for recording, evaluating, follow-up, and reporting AEs and SAEs are outlined in Section 10.3.

Before any infusion is started, the treating physician and other appropriate personnel must make certain that medication (i.e., adrenaline, inhaled beta agonists, antihistamines, corticosteroids) and other equipment to treat anaphylaxis are readily available. The infusion must be stopped immediately if Grade  $\geq 2$  allergic/hypersensitivity reactions (including drug fever) or Grade  $\geq 3$  cytokine release syndrome/acute infusion reaction occurs. The Sponsor must be notified within 24 hours of any infusion reaction requiring interruption or discontinuation of study drug or meet the criteria of AESI.

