Infusion-related reaction	Mild transient reaction; infusion interruption not indicated; intervention not indicated	Therapy or infusion interruption indicated but responds promptly to symptomatic treatment (eg, antihistamines, non-steroidal anti-inflammatory drugs [NSAIDs], narcotics, IV fluids): prophylactic medications indicated for ≤ 24 hours	Prolonged (eg, not rapidly responsive to symptomatic medication and/or brief interruption of infusion); recurrence of symptoms following initial improvement, hospitalization indicated for clinical sequelae	Life-threatening consequences; urgent intervention required	Death	
Allergic reaction	Transient flushing or rash, drug fever < 38.0°C. Intervention not indicated	Therapy or infusion interruption indicated but responds promptly to symptomatic treatment (eg, antihistamines, NSAIDs, narcotics, IV fluids): prophylactic medications indicated for ≤ 24 hours	Prolonged (eg, not rapidly responsive to symptomatic medication and/or brief interruption of infusion); recurrence of symptoms following initial improvement, hospitalization indicated for clinical sequelae (eg, renal impairment, pulmonary infiltrates)	Life-threatening consequences; urgent intervention required	Death	
Anaphylaxis	-	_	Symptomatic bronchospasm, with or without urticarial; parenteral intervention indicated; allergy-related edema/angioedema; hypotension	Life-threatening consequences; urgent intervention required	Death	
Cytokine release syndrome	Mild reaction; infusion interruption not indicated; intervention not indicated	Therapy or infusion interruption indicated but responds promptly to symptomatic treatment (eg, antihistamines, NSAIDs, narcotics, IV fluids): prophylactic medications indicated for ≤ 24 hours	Prolonged (eg, not rapidly responsive to symptomatic medication and/or brief interruption of infusion); recurrence of symptoms following initial improvement, hospitalization indicated for clinical sequelae (eg, renal impairment, pulmonary infiltrates)	Life-threatening consequences; pressor or ventilator support indicated	Death	

Abstracted from NCI CTCAE Version 5.0.

Abbreviations: IV = intravenous; NSAIDs = nonsteroidal anti-inflammatory drugs

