8.7. Extent of Exposure

Exposure data will be summarized by total dose administered (mg), total volume administerd (mL) and the number of interruptions (SC Infusion). Study drug administration data will be listed.

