11.1.2. Analysis of the Endpoints

The endpoint regarding the quantitative assessment of immunogenicity between Japanese and non-Japanese healthy participants cannot be analyzed due to early termination of the study.

ADA and NAb data reporting

- Incidence, titer, duration, time to detection, pre-existing ADA
- PK concentration or parameter by immunogenicity response
- PD response by immunogenicity response
- Individual PK data listing or spaghetti plots with ADA category overlaid.
- For ADA categories and participants, summary of individual plots of PK, PD, ADA titer, and NAb time course to better understand the clinical impact of immunogenicity at a subject level.

12. Safety

The population used for safety analyses will be the Safety Set.

Safety analyses will include an analysis of all treatment-emergent adverse events (TEAEs), SAEs, AESIs, ECGs, clinical laboratory data, physical examinations, and vital sign measurements using descriptive statistics.

No inferential statistical analyses are planned on the safety parameters of this study.

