12.1. Adverse Events / Adverse Drug Reactions

AEs for all participants in the Safety Set will be included in the AE summaries.

Adverse events will be summarized by system organ class (SOC) and preferred term (PT) for each treatment and overall, based on the MedDRA dictionary version 23.1.

If the relationship to study drug is missing for TEAEs, then the relationship will be counted as related to study product for the summary tables. Missing severity for TEAEs will be counted as Grade 3.

Pretreatment AEs are defined as AEs that were reported or worsened after signing the ICF up to the start of study drug dosing. Treatment-emergent AEs are defined as AEs that were reported or worsened on or after the start of study drug dosing through the safety follow-up visit.

If the start date of an AE is partially or completely missing, the date will be compared as far as possible with the date of the start of administration of study drug. The AE will be assumed to be treatment-emergent if it cannot be definitively shown that the AE did not occur or increase in severity during the treatment period (worst case approach). The following general rules will be used:

- If the start day is missing but the start month and year are complete, an AE will not be considered as being treatment-emergent only if the start month/year is before the month/year of the first study drug administration.
- If the start day and month are missing but the start year is complete, an AE will not be considered as being treatment-emergent only if the start year is before the year of the first study drug administration.
- If the start date is completely missing, an AE will be considered treatment-emergent unless the stop date is before the first study drug administration.

Duration will be calculated for AEs that resolve as the difference between the resolution date and onset date plus 1 and expressed in days. Should an AE have a short duration (*i.e.* < 24 hours), the duration will be calculated as the difference between the resolution time and the onset time.

Adverse events of special interest are defined as any IRR equal to or higher than Grade 3; or any IRR that may jeopardize the participant and requires immediate intervention to prevent it from leading to severe outcomes. Potential cases of any delayed hypersensitivity reactions, equal to or higher than Grade 2.

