Only TEAEs will be included in the summary tables, however separate listings for treatment-emergent and non-treatment-emergent AEs will be generated. Additional listings will be provided for deaths, AESIs, serious AEs and Adverse Events Leading to Study Drug Discontinuation.

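### Short infusion-site reactions not recorded as IRRs have no planned incidence by arm: Protocol 8.2.9 keeps those of 24 h or less out of the AE data, with unclear scope, and SAP Section 12 plans no infusion-site summary

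*Protocol*

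**What the plan says.** **The exemption.** Protocol 8.2.9 has infusion sites evaluated at the times in the schedule of activities. It then says that infusion-site reactions "will not be listed as an AE unless they persist for more than 24 hours". Induration of up to 1 cm is given as an example; no limit on type, size or grade follows.

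**The AE definition.** Protocol 10.3.1 counts any untoward medical occurrence as an AE, with no minimum duration. Its list of events that are not AEs does not mention short infusion-site reactions.

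**The IRR route.** Protocol 8.3.5.1 includes among IRR symptoms "urticaria, edema, nausea, and all types of rashes". Protocol 10.4 says "All infusion-associated reactions will be reported to the Investigator and qualified designee", and its Table 20 grades as 1 a "Mild transient reaction; infusion interruption not indicated; intervention not indicated".

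**The analysis.** SAP Section 12 covers TEAEs, "SAEs, AESIs, ECGs, clinical laboratory data, physical examinations, and vital sign measurements using descriptive statistics". SAP 12.1 adds "Only TEAEs will be included in the summary tables", and Protocol 9.4.1 has the same restriction. No part of SAP Section 12 mentions infusion-site evaluations.

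**The concern.** The primary objective is the safety and tolerability of SC dosing, and each infusion is followed by scheduled inspection of the site. A recording rule nevertheless keeps reactions of 24 h or less out of the AE data, and no separate table reports them. Following the plan exactly, the report could not say how many participants on ALXN1830 or on saline had a short local reaction, unless it was also recorded as an IRR. A reader could take a low count of local TEAEs as evidence of good local tolerability when the recording rule may have contributed to it.

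**Working it through.** The plan states no figure on this point, so the check is mainly a comparison of sections.

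**1. Schedule against threshold.** In the schedule of activities (Protocol 1.3), site evaluations fall at end of infusion, 2, 4, 12 and 24 h after intensively sampled doses, and at end of infusion, 2 and 24 h after the others. The last is at 24 h ± 1 h, timed from the start of infusion. A reaction that begins after the infusion has started has therefore usually lasted no more than 24 h when last inspected on schedule. Whether it passes the threshold depends on later follow-up. The table footnote that extends evaluation until resolution is worded for IRRs; AE monitoring is otherwise continuous.

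**2. Where a local finding can appear.**

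| Finding | Planned output |
|---|---|
| Site reaction lasting more than 24 h | TEAE tables |
| Short reaction recorded as an IRR | TEAE tables by SOC, PT, grade and relationship (SAP 12.1); AESI table if it meets that definition |
| Short reaction within the exemption, not recorded as an IRR | Listing at most (Protocol 9.4, SAP 7.1) |

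The third row is the gap. Its size depends on two things the documents leave open: how wide the exemption is, and when a short local finding is an exempt site reaction rather than a recordable IRR.

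**3. Other outputs.** SAP 8.7 summarises infusion interruptions, SAP 8.5 concomitant medication, and SAP 12.5 lists physical examinations. None gives an incidence of site findings. SAP 12.2 and 12.5 do name what is to be listed only, such as drug screens and physical examinations; infusion-site evaluations are not named in either way.

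**4. Why size and direction are open.** Let p be the share of participants in an arm with any local reaction. Let s be the share of those whose reactions all resolve within 24 h, fall under the exemption and are not recorded as IRRs. The incidence visible in the AE tables is p × (1 − s). The documents give neither quantity, so the values below are assumptions for illustration only, with p = 50% on active and 30% on saline, a true difference of 20 points.

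- s = 80% active, 50% saline: 50% × 0.2 = 10% against 30% × 0.5 = 15%. The difference reverses, to −5 points.
- s = 50% active, 80% saline: 50% × 0.5 = 25% against 30% × 0.2 = 6%. The difference is 19 points, almost unchanged.
- s = 50% active, 100% saline: 25% against 0%. The difference widens to 25 points.

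The rule can shrink, reverse or widen the visible difference, depending on durations that are not given.

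**The case against.** The strongest reply is that the SAP follows the protocol. Infusion-site evaluation is not a named component of the primary endpoint (SAP 5.1) and is not in Protocol 9.4.1. Protocol 9.4 allows data to be shown in listings or tabulations, so a listing alone satisfies it. This stands: a reader might infer a departure from the endpoint list or a loss of data, and the documents support neither. What is missing is a summary.

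Second, a reader might infer that mild IRRs go unreported because only the more serious ones are of special interest ("Adverse events of special interest are defined as any IRR equal to or higher than Grade 3", or needing immediate intervention). That is not so. A Grade 1 or 2 IRR recorded as an AE enters several TEAE tables by cohort and for pooled placebo. The gap is confined to short reactions not so recorded.

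Third, the size cap in the example fits an exemption for minor reactions at least as well as one for all reactions, and a specific rule can qualify a general definition. This too is fair. The text does not settle it, so one may not assert that every site reaction is exempt.

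Fourth, the CRF is not shown, so it is unknown whether structured site findings exist to tabulate. This limits the remedy but does not answer the point: none of the remaining routes gives an incidence by arm.

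**Conclusion.** The concern holds in this limited form. As written, the plan yields no incidence by arm of infusion-site reactions that last 24 h or less, fall within the exemption and are not recorded as IRRs. It is a gap in the tolerability summary for the primary objective, worth closing because the remedy is cheap. A reader might go further and infer that the plan flatters ALXN1830 against saline. The documents do not support that: the rule applies to both arms, no rates or durations are given, and neither the size nor the direction of any effect can be determined. The conclusion rests on the current text of both documents and on no infusion-site output being specified elsewhere.

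**What to change.** **Table.** Add to SAP Section 12 one descriptive Safety Set table, as far as the CRF data allow, of participants with any infusion-site finding, by cohort for active and for placebo, with the number of infusions shown. Besides the pooled placebo column, split placebo by single-dose, 4-dose and 12-dose regimen, because the pooled column mixes participants with 1, 4 and 12 infusions.

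**Statement.** Say in the SAP and CSR that the TEAE tables exclude infusion-site reactions of 24 h or less unless recorded as IRRs, with the scope of that exclusion as clarified. This documents how the AE data were formed; it does not change AE collection or AE counts.

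**Reconciliation.** Protocol 8.2.9, 10.3.1, 8.3.5.1 and 10.4 must be reconciled on how far the exemption reaches and on how a short local finding is classed.

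**Cost.** One extra table with small cells. Assuming the planned 6:2 allocation, full Cohorts 1, 3, 4 and 5 and no replacements, the placebo cells hold 2 single-dose participants (Cohort 1), 2 + 2 = 4 on 4 doses (Cohorts 4 and 5) and 2 on 12 doses (Cohort 3). SAP 4.1 reports only 2 participants in Cohort 2, with arm not stated, and none in Cohort 6. The split is for description only, and the infusion counts are context rather than a basis for rates.

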#### **8.3.** Adverse Events and Serious Adverse Events

The definitions of AEs and SAEs and specific reporting requirements can be found in Section 10.3.

All AEs will be reported to the Investigator or qualified designee by the participant (or, when appropriate, by a caregiver, surrogate, or the participant's legally authorized representative).

The Investigator and any qualified designees are responsible for detecting, documenting, and recording events that meet the definition of an AE or SAE and remain responsible for following up AEs that are serious, considered related to the study drug or study procedures, or that caused the participant to discontinue the study drug (see Section 7).

Procedures for recording, evaluating, follow-up, and reporting AEs and SAEs are outlined in Section 10.3 (Appendix 3).

#### 8.3.1. Time Period and Frequency for Collecting AE and SAE Information

All AEs and SAEs will be collected from the signing of the ICF until the follow-up visit at the time points specified in the SoA (Section 1.3).

All SAEs will be recorded and reported to Alexion or the designee immediately and under no circumstance should this exceed 24 hours, as indicated in Section 10.3. The Investigator will submit any updated SAE data to Alexion within 24 hours of it being available.

Investigators are not obligated to actively seek AEs or SAE data after conclusion of the study participation. However, if the Investigator learns of any SAE, including a death, at any time after a participant has been discharged from the study, and he/she considers the event to be reasonably related to the study drug or study participation, the Investigator must promptly notify Alexion.

## **8.3.2.** Method of Detecting AEs and SAEs

The method of recording, evaluating, and assessing causality of AEs and SAEs and the procedures for completing and transmitting SAE reports are provided in Section 10.3.

Care will be taken not to introduce bias when detecting AEs and/or SAEs. Open ended and non-leading verbal questioning of the participant is the preferred method to inquire about AE occurrences.

#### 8.3.3. Follow-up of AEs and SAEs

After the initial AE/SAE report, the Investigator is required to proactively follow-up on each participant at subsequent visits/contacts. All SAEs will be followed up until resolution, stabilization, the event is otherwise explained, or the participant is lost to follow-up (as defined in Section 7.4) Further information on follow-up procedures is provided in Section 10.3.

#### 8.3.4. Regulatory Reporting Requirements for SAEs

- Prompt notification of an SAE by the Investigator to Alexion is essential so that legal obligations and ethical responsibilities towards the safety of participants and the safety of a study drug under clinical investigation are met.
- Alexion has a legal responsibility to notify both the local regulatory authority and other regulatory agencies about the safety of a study drug under clinical investigation. Alexion will comply with country-specific regulatory requirements relating to safety reporting to the regulatory authority, IRBs/IECs, and Investigators.
- Suspected unexpected serious adverse reactions (SUSARs) must be reported
  according to local regulatory requirements and Alexion policy and forwarded to
  Investigators as necessary.

• An Investigator who receives an Investigator safety report describing an SAE or other specific safety information (eg, summary or listing of SAEs) from Alexion will review and then file it along with the IB and will notify the IRB/IEC, if appropriate according to local requirements.

#### 8.3.5. Adverse Events of Special Interest

Any nonserious AE of special interest (AESI) is required to be reported by the Investigator to Alexion immediately ( $\leq$  24 hours after learning of the AESI). The AESI will be documented in the safety database and a narrative will be required for each event.

The AESIs for ALXN1830 include the following:

- Any IRR equal to or higher than Grade 3; or any IRR that may jeopardize the participant and requires immediate intervention to prevent it from leading to severe outcomes.
- Potential cases of any delayed hypersensitivity reactions, equal to or higher than Grade 2.

#### 8.3.5.1. Infusion-Related Reaction

Infusion-related reactions to mAbs include both immune mediated and non-immune mediated reactions. Symptoms of IRRs may include flushing, alterations in heart rate and BP, dyspnea, bronchospasm, back pain, fever, urticaria, edema, nausea, and all types of rashes. Anaphylaxis is recognized as a severe, life-threatening, generalized, or systemic reaction. IRRs usually develop during drug infusion, or within hours of infusion, although may be delayed for up to 24 hours. Most IRRs are mild to moderate in severity.

Refer to Section See Section 10.4 for guidance on management of IRRs.

#### **8.3.5.2.** Non-acute Hypersensitivity Reaction

Non-acute hypersensitivity (ie, serum sickness) and immune responses secondary to IC formation typically have a subacute presentation (FDA, 2014). Clinical signs may include delayed onset of fever, rash, arthralgia, myalgia, hematuria, proteinuria, and serositis, in the face of an ongoing antibody response to the study drug (Hunley, 2004). Assessment of AE causality will likely require evaluation of CICs and complement activation.

## **8.4.** Treatment of Overdose

An overdose is defined as a significant variation above the recommended/scheduled dosage for a product. The dosing for this study will be conducted in a controlled clinical setting and an overdose is not anticipated. However, in the event of an accident, for this study, an overdose of ALXN1830 is considered any dose of ALXN1830 greater than 2250 mg.

Overdoses are medication errors that are not considered AEs unless there is an untoward medical occurrence resulting from the overdose.

In the event of an overdose, the Investigator should:

- Contact the Medical Monitor immediately.
- Closely monitor the participant for any AE/SAE and laboratory abnormalities until IgG levels have returned to normal.
- Follow-up until ALXN1830 can no longer be detected systemically or IgG levels have returned to Baseline.
- Document the quantity of the excess dose as well as the duration of the overdose in the CRF.

Decisions regarding dose interruptions or modifications will be made by the Investigator in consultation with the Medical Monitor based on the clinical evaluation of the participant.

